6.3 Case Report Forms (CRF) and Subject Activities

[figure not shown]
Table 1: Case Report Forms and Study Activities

Activity	Study Visit				
	Screening/ Roll-In	Treatment	Follow-up Visits	Final Follow-up	Confirm
Visit Timing	Week 1	Week 3	Weeks 4-13	Week 14	Week 15
Informed consent	X				
Inclusion Exclusion Criteria [CRF]	X				
Demographics, Medical Conditions, and Medical Co-Morbidities [CRF]	X				
SF-36 Health Survey [CRF]	X			X ¹	X
Wound Assessment and Treatment [CRF]		X	X	X	X
Subject Discontinuation [CRF]		As Needed			
Wound Tissue Sample	X			X ¹	
Wound sharp debridement	X	X	As Needed		
Wound Closure Assessment		X	X	X	X
Wound E-Z Graph assessment [CRF]	X	X	X	X	
Wound photograph	X	X	X	X	X
Wound Dressing and Care Instruction	X				
Subject Per Diem			X	X	X
Off-Loading Device Fitting and Instruction	X				

Activity	Study Visit				
	Screening/ Roll-In	Treatment	Follow-up Visits	Final Follow-up	Confirm
Visit Timing	Week 1	Week 3	Weeks 4-13	Week 14	Week 15
Nutrition Instruction	X				
MIRODERM Application		X	As Needed		
Adverse Event [CRF]			As Needed		
Protocol Deviation [CRF]			As Needed		

¹For subjects who have not completely healed

6.4 Subject Study Flow Chart

6.5 Assessment and Roll-In Visit (Visit 1; Week 1)

6.5.1 Recruitment and Informed Consent

Male and female patients between 18 and 80 years old (inclusive) who suffer from a persistent neuropathic DFU will be recruited from the investigators practice and network. Patients will have a moderate sized ulcer that has not fully closed during the previous 3 months and who have received at least two attempts using biological solutions. Patients may present with multiple ulcers; however, only a single ulcer per subject will be selected for evaluation in the study protocol.

An assessment of the inclusion and exclusion criteria will be undertaken. All items assessed in the inclusion and exclusion criteria are tests or observations that would be known or obtained as standard of care regardless of the patient's participation in this study. Those patients which appear to be appropriate for the study will be asked to participate and undergo an informed consent procedure. Patients will undergo the informed consent process. At this time, the study procedures, subject expectations and the approved Informed Consent Form (ICF) will be reviewed with the patient. The patient will be given an opportunity to discuss the study with the investigator, including any medical

aspect of their pathology and treatment. The patient will be encouraged to ask questions and will have all of their questions addressed to their satisfaction before deciding whether or not to be in the study.

6.5.1.1 *Signing the Informed Consent Form*

If the patient agrees to participate in the study, the patient will sign the consent form and will be provided with a copy for their records. ***Upon signing the consent form the patient will be considered an active subject in the study but not yet enrolled. The subject will be considered enrolled after treatment with MIRODERM.***

6.5.2 Inclusion criteria

To be included in this study, subjects must:

- Be 18 years old or older at time of initial study visit
- Have Type I or Type II diabetes
- Be willing and able to sign an informed consent
- Have a neuropathic DFU with the following characteristics:
 - Is equal to or greater than 1 cm² and less than or equal to 12 cm²
 - Has failed to close following at least 2 treatments with a biologic
 - Has been present for 90 days or longer
 - Does not show signs of infection
 - Is full thickness (Wagner Grade I or II)
 - Located distal to the malleolus
 - Depth of less than or equal to 5 mm
 - No exposed capsule, tendon or bone
 - No tunneling, undermining or sinus tracts
 - Not between the toes
- Be willing and able to maintain required off-loading of affected limb
- Be willing and able to perform necessary dressing changes
- Have at least one of the following:
 - An Ankle-brachial index ≥ 0.8
 - TcPO₂ of ≥ 30 mmHg
 - A toe pressure of ≥ 50 mmHg

6.5.3 Exclusion criteria

To be included in this study, subjects must not:

- Be pregnant or be planning to become pregnant during the study
- Have had a Chopart's Amputation (or higher)
- Have a history of bone cancer of the affected limb
- Be undergoing dialysis
- Have active osteomyelitis or be receiving treatment for osteomyelitis
- Be diagnosed with unstable Charcot Foot on the affected side
- Have an HbA1c level of $\geq 12\%$ within the past 90 days
- Have another ulcer within 2 cm of the study ulcer
- Be immunocompromised or at risk of immunosuppression as determined by the treating investigator
- Have a known collagen vascular disease or connective tissue disease
- Have received treatment of the study ulcer with a skin substitute product or topical growth factor within the past 4 weeks

- Be participating in another medical research study
- Have a sensitivity to porcine material

6.5.4 Health Survey

Subjects will complete a SF-36v2® Health Survey

6.5.5 Demographics, Medical Conditions and Co-morbidities

Investigator will document subject characteristics in the medical chart and on the appropriate case report forms including but not limited to:

- Demographics
- Current medical conditions
- Wound history and assessment
- Co-morbidities and general medical history

6.5.6 Wound Tissue Sample

Two tissue sections of at least 2mm will be retained from the debridement material for later analysis.

6.5.7 Wound treatment – Sharp debridement

The wound will be debrided, to the level of viable bleeding tissue, as necessary using sharp debridement. Other types of debridement (ultrasonic, enzymatic, larval, etc.) are not permitted.

6.5.8 Wound size documentation

The wound area will be documented using the E-Z Graph Wound Assessment System and photography.

6.5.9 Wound treatment – Dressing

Wound will be dressed per standard of care. Treatment dressing will include saline hydrogel to maintain moisture, a primary gauze layer and roll gauze as secondary covering. Subjects will be instructed on care of the wound and dressing and instructed to change the wound dressing every day during the Assessment Roll-In phase.

6.5.10 Off-Loading Device fitting and instruction

Subject will be fitted with an off-loading device and given instruction on use.

6.5.11 Proper Nutrition Instruction

Subjects will be given instruction on proper nutrition consistent with Cleveland Clinic's *Nutritional Guidelines to Improve Wound Healing* (2014, Cleveland Clinic) , and will be given a copy of the guidelines.

6.6 Treatment Visit (Visit 2; Week 3)

6.6.1 Wound Closure Assessment

Wound will be assessed for closure. If wound is closed subjects will receive no further treatment, have their wound size documented (per 6.8.2), and will be asked to return in 1-week for a confirmation visit.

6.6.2 Wound treatment – Sharp debridement

The wound will be debrided, to the level of viable bleeding tissue, as necessary using sharp debridement. Other types of debridement (ultrasonic, enzymatic, larval, etc.) are not permitted.

6.6.3 Wound assessment and size documentation

Wound will be assessed for gross dimensions and infection. If an infection is present an AE form should be completed and ***the subject will be discontinued from the study.***

The area of the wound will be documented using the E-Z Graph Wound Assessment System and photography.

6.6.4 Wound treatment – MIRODERM application and dressing

MIRODERM Biological Wound Matrix will be applied consistent with the IFU and wound will be dressed. An appropriate size of MIRODERM will be placed over the wound and, as needed, bolstered such that MIRODERM comes into contact with the maximum amount of wound surface. MIRODERM should be secured with Steri-strips, sutures or staples. Primary dressing shall have a non-adherent wound contact layer. Secondary dressing shall be roll gauze. No other biological material shall be used. ***Subjects will be considered enrolled into the study subsequent to treatment with MIRODERM Biologic Wound Matrix.*** Treatment details will be recorded.

6.7 Follow-up Visits (Visits 3-14; Weeks 4-15)

6.7.1 Wound Closure Assessment

Wound will be assessed for closure. If wound is closed subjects will receive no further treatment, have their wound size documented (per 6.8.2), and will be asked to return in 1-week for a confirmation visit.

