
Schedule of Visits
	
 1 Assessment and Roll-in (2-weeks prior to procedure) 2 Index Procedure 3 1-Week post-procedure (\pm 2 days) 4 2-Week post-procedure (\pm 2 days) 5 3-Week post-procedure (\pm 2 days) 6 4-Week post-procedure (\pm 2 days) 7 5-Week post-procedure (\pm 2 days) 8 6-Week post-procedure (\pm 2 days) 9 7-Week post-procedure (\pm 2 days) 10 8-Week post-procedure (\pm 2 days) 11 9-Week post-procedure (\pm 2 days) 12 10-Week post-procedure (\pm 2 days) 13 11-Week post-procedure (\pm 2 days)

	
14 12-Week post-procedure (\pm 2 days)
 
15 Confirmation: 13-Week post-procedure (\pm 2 days)
 
All subjects will be offered a \$25 gift card for completing weekly follow-up during the treatment phase.

Study Duration	1 Year
Assessment Tools	
Ankle Brachial Index
 
HbA1c
 
Monofilament test for neuropathy
 
Photograph
 
E-Z Graph Wound Assessment System
 
Sf-36v2 Health Survey

Primary Endpoint	Proportion of subjects who have a closed wound at or before 12 weeks after the index procedure.
Primary Hypothesis	
As an observational study, there is no formal hypothesis test. The precision of the estimate of the proportion of subjects who successfully close will be determined.
 
Assumptions:
 
 • A minimum 50 subjects • A 95% Confidence Interval of the estimate • A 2-sided confidence interval • Using exact Clopper-Pearson estimation 
The Confidence Intervals (CI) at selected success rates are as follows:
 
 • @ 25%; CI = 25.4% Boundaries 13.8%-39.3% • @ 50%; CI = 28.9% Boundaries 35.5%-64.5% • @ 75%; CI = 25.4% Boundaries 60.7%-86.2% 
Thus, a sample size of 50 should allow for a reasonable estimate of treatment success at 12 weeks and for reasonable comparisons to historical controls.

Statistical Analysis	
Descriptive statistics including but not limited to mean, standard deviation, frequency and percentages will be used to describe demographics, medical history, and characterize baseline variable as appropriate.
 
A Z-test will be used to assess whether the proportion of subjects that were successful is greater than zero. Kaplan-Meier analysis will be used describe the survival curve assuming complete closure as the event of interest. A repeated measure ANOVA will be used to assess changes in, wound area and quality of life over time.

TABLE OF CONTENTS

1	Background	13

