6.8 Confirmation Visit (1 week after complete closure or Visit 15; Week 16)

6.8.1 Wound Closure Assessment

Wound will be assessed for closure. If wound is still closed subject will continue to 6.8.2 below. ***If it is determined that the wound is reopened,*** subject will have wound assessed (6.7.2) and treated as needed (6.7.3). Subject will continue in the follow-up phase (6.7) until wound is closed or 12 weeks of follow-up have been completed.

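### Table 1 (6.3) places the final follow-up 11 weeks after treatment, while 6.7, 6.8, the synopsis visit list and the primary endpoint all require 12

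*Combined protocol and SAP*

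**What the plan says.** Table 1 (section 6.3, case report forms and activities by visit) has a Visit Timing row. Screening is Week 1 and treatment is Week 3. The remaining columns, for follow-up visits, final follow-up and confirmation, read "Weeks 4-13 Week 14 Week 15". The row is printed twice, where the table continues, with the same figures.

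The section headings number the visits from the same start:

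- 6.5: "Assessment and Roll-In Visit (Visit 1; Week 1"
- 6.6: "Treatment Visit (Visit 2; Week 3"
- 6.7: "Follow-up Visits (Visits 3-14; Weeks 4-15"
- 6.8: "Confirmation Visit (1 week after complete closure or Visit 15; Week 16"

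The synopsis visit list counts from the procedure. It has twelve weekly follow-up visits, each with a window of 2 days either side. The last (Visit 14) is at 12 weeks, and confirmation (Visit 15) is at 13 weeks. The synopsis defines the primary endpoint as "Proportion of subjects who have a closed wound at or before 12 weeks after the index procedure", and section 4.2 uses the same 12-week limit.

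**The concern.** Table 1 and sections 6.5 and 6.6 agree on Week 1 and Week 3, then part company: Table 1 ends follow-up one week before 6.7 does and confirms one week before 6.8 does. The visit in dispute is the last assessment that can contribute to the primary endpoint.

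Table 1 is the activity schedule, so a site may well book visits from it. Its final follow-up column carries the closing SF-36 and the second tissue sample for subjects who have not healed. A site using those week labels could carry out the final-visit procedures and exit a subject with an open wound at 11 weeks. A closure that would first have been seen at 12 weeks would then go unrecorded, and follow-up would be shorter for those subjects than for subjects booked from the synopsis list.

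**Working it through.** **Inputs.** Treatment is Week 3 (Table 1 and 6.6). Final follow-up is Week 14 and confirmation Week 15 (Table 1). The last follow-up is Week 15 (6.7) and confirmation Week 16 (6.8). The visit window is ±2 days (synopsis).

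**Weeks after treatment = visit week − 3.**

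| Visit | Table 1 | 6.7 / 6.8 | Synopsis list |
|---|---|---|---|
| Last follow-up | 14 − 3 = 11 | 15 − 3 = 12 | 12 |
| Confirmation | 15 − 3 = 12 | 16 − 3 = 13 | 13 |

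**Number of weekly follow-up visits.** Table 1: Weeks 4 to 13 are 10 visits, plus Week 14, giving 11. Section 6.7: Weeks 4 to 15, or Visits 3 to 14, give 12. The synopsis list also gives 12.

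**Does the window absorb the difference?** An 11-week visit can fall no later than day 77 + 2 = 79. A 12-week visit can fall no earlier than day 84 − 2 = 82. The two do not overlap.

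**Does another week origin explain the row?** With elapsed weeks from screening (screening 0, treatment 2), the 12-week visit is 2 + 12 = 14 and confirmation is 2 + 13 = 15. These are Table 1's last two labels. But the same row prints screening as Week 1, treatment as Week 3 and the first follow-up as Week 4, so it does not use that origin throughout. The likely explanation is a change of origin partway along the row.

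**Possible size.** The documents give no weekly closure rate, so this is an illustration. Assume a constant weekly rate, and assume that a subject exited open at 11 weeks is counted as not closed. If p is the true proportion closed by 12 weeks, the proportion closed by 11 weeks is 1 − (1 − p)^(11/12). The values of p are the three success rates in the protocol's sample size justification.

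| p at 12 weeks | Closed by 11 weeks | Loss (points) |
|---|---|---|
| 25% | 23.2% | 1.8 |
| 50% | 47.0% | 3.0 |
| 75% | 71.9% | 3.1 |

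If all 50 subjects were booked from Table 1, that would be 0.018 × 50 = 0.9 to 0.031 × 50 ≈ 1.5 closures. If none were, it would be zero. The protocol's own 95% intervals at n = 50 are 25.4 to 28.9 points wide.

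**The case against.** The strongest reply is that Table 1 does not set the stopping rule. It lists discontinuation only as needed. The text that ends participation for an unhealed subject is elsewhere (synopsis design section, 6.1, 6.2 and 6.9), and each statement is set at 12 weeks. Section 6.7 ties the closing procedures to the 12-week post-treatment visit, and 6.8.1 returns reopened wounds to follow-up until 12 weeks are complete. The synopsis already lists every visit by weeks after the procedure. A site that exited an open wound at 11 weeks would be contradicting all of this.

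The stated maximum participation of 15 weeks also fits 2 + 12 + 1 elapsed weeks, which supports a labelling slip and not a plan for 11 weeks of follow-up. Nor is there a formal hypothesis about the closure proportion whose outcome a small loss might alter.

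Most of this stands. A reader might infer from Table 1 that follow-up is planned for only 11 weeks, or that the 12-week endpoint will be missed or measured over different lengths at different sites. The documents do not support that: the endpoint, the exit rules and the visit list all agree on 12 weeks. What the reply does not remove is the printed contradiction. Sites see the labels and not the reason behind them, and on its own numbering the row puts the final visit at 11 weeks.

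**Conclusion.** The contradiction is certain and is confined to the Visit Timing row of Table 1, which is one week short of 6.7, 6.8 and the synopsis list for the final follow-up and confirmation. The text of 6.7 and 6.8 is consistent with the endpoint.

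The consequence is conditional on a site booking from Table 1. For subjects so booked, the expected direction is an under-count of closures, by roughly 2 to 3 percentage points under the constant-rate assumption and if those subjects are counted as not closed. The documents give neither a closure rate nor the share of subjects who would be affected, so the trial-level effect runs from zero up to that figure, which is small beside the planned interval width. The point merits correction because it concerns the timing of the primary endpoint visit, but it is a schedule inconsistency and not a flaw in the endpoint.

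**What to change.** Reconcile the Visit Timing row of Table 1 with 6.6, 6.7, 6.8 and the synopsis visit list, so that the final follow-up column matches the endpoint's own 12-week definition and confirmation follows one week later. Preferably label the columns by weeks after the index procedure, as the synopsis does, which removes the ambiguity over where the count starts.

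The cost is one corrected table row in a minor protocol clarification. If sites are already active, tell them of the change and check whether any unhealed subject was exited at the Table 1 week.

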6.7.2 Wound assessment and size documentation

Wound will be assessed for gross dimensions and infection. If an infection is an AE form should be completed and ***the subject will be discontinued from the study.***

The area of the wound will be documented using the E-Z Graph Wound Assessment System and photography.

6.7.3 Wound treatment – Sharp debridement and MIRODERM application

If clinically indicated, the wound will be debrided, to the level of viable bleeding tissue, as necessary using sharp debridement. MIRODERM Biological Wound Matrix will be reapplied consistent with 6.6.4 and the IFU. Treatment details will be recorded.

6.7.4 Follow-up Stipend

Subjects will receive a \$25 gift card at each follow-up. Distribution of gift card will be documented.

The following activities will be completed by subjects who present at the 12-week post-treatment visit and have a wound that is not fully closed.

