4.3 Secondary Objectives

Some secondary objectives include but are not limited to:

- Describe the time course to full wound closure
- Determine the subjects' quality of life score before and after treatment
- Characterize the safety profile of MIRODERM and the procedure
- Explore the histological characteristics of those who successfully heal and those who don't

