If wound has not closed, the dressing will be changed (subsequent to any needed treatment as described in the above paragraph) and the subject will return the following week. If the wound is healed subject will return for a confirmation visit one week later. If, after 12 weeks, the wound is not healed, subject will complete a SF-36 quality of life survey, two tissue sections of at least 2mm from the wound area will be collected and the subject will be discontinued from the study per protocol.

Confirmation Phase

Subject will complete a quality of life assessment and have their wound area photographed. Physician will confirm the wound is still closed and the subject will be discontinued per protocol. If wound has reopened subject will return to the treatment phase.

Subjects whose wound has been assessed closed will return for a confirmation visit. The wound will be assessed for closure. If the wound is still closed, the wound area will be photographed, the subject will complete a SF-36 quality of life survey and be discontinued from the study per protocol. If wound has reopened, subject will return to the follow-up phase at the appropriate post-treatment week continuing there until wound closure or through 12 weeks of follow-up as described in “Treatment Phase” above.

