7 STATISTICAL CONSIDERATIONS

As a prospective clinical outcome and survivorship study, there are no specific hypotheses to be tested. Data analysis may be conducted intermittently as needed or as requested by investigators without a power penalty and consist primarily of summary statistics and inferential statistics for changes in dependent measures over time.

Specific data analyses may include but are not limited to:

- **Demographics** and other pre-treatment characteristics will be summarized and characterized with appropriate descriptive statistics including error measures. Statistics may include mean, mode, median, range, inter-quartile range, minimum, maximum, frequency, cumulative frequency percentage and cumulative percentage. Results may be presented in a narrative and graphically.
- **Subject reported and dependent outcome measures** will be summarized and thoroughly characterized with the appropriate descriptive statistics including error measures. Statistics may include mean, mode, median, range, inter-quartile range, minimum, maximum, frequency, cumulative frequency percentage and cumulative percentage. Results may be presented in a narrative and graphically. Measures collected at multiple timepoints will also be analyzed using inferential statistics to assess changes over time, of special interest post-treatment changes from pre-treatment values. As appropriate a repeated measure ANOVA or Wilcoxon signed rank

test will be completed for each outcome measure. If a significant trend is identified, significance among time points may be further explored using the appropriate pair-wise comparisons. In all cases a p-value equal to or less than 0.05 will be considered significant. No corrections for multiple pair-wise comparisons will be made.

Missing data will be ignored in statistical calculations while using the appropriate n (sample size) for any given statistic or test.

Sample Size Justification: The precision of the estimate of the proportion of subjects who successfully close will be determined.

Assumptions:

- A minimum 50 subjects
- A 95% Confidence Interval of the estimate
- A 2-sided confidence interval
- Using exact Clopper-Pearson estimation

The Confidence Intervals (CI) at selected success rates are as follows:

- @ 25%; CI = 25.4% Boundaries 13.8%-39.3%
- @ 50%; CI = 28.9% Boundaries 35.5%-64.5%
- @ 75%; CI = 25.4% Boundaries 60.7%-86.2%

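### No SF-36 is planned when a subject exits for infection or osteomyelitis, and the texts conflict on whether a wound that reopens at Week 13 gets one

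*Combined protocol and SAP*

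**What the plan says.** Weeks here count from the index MIRODERM application.

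The secondary objective in 4.3 is to "Determine the subjects' quality of life score before and after treatment". The baseline SF-36 is taken at Visit 1 (6.5.4). A second one can arise in two ways.

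- **Week 12 visit, wound open.** The text that leads into 6.7.5 reads "The following activities will be completed by subjects who present at the 12-week post-treatment visit and have a wound that is not fully closed". The footnote to Table 1 restricts the final follow-up survey in the same way.
- **Confirmation visit.** The first Confirmation Phase paragraph of 6.1 sets no condition: "Subject will complete a quality of life assessment and have their wound area photographed". The synopsis says the same, and the Confirm column of Table 1 carries an X without a footnote. The second Confirmation Phase paragraph of 6.1 does set a condition: "If the wound is still closed, the wound area will be photographed, the subject will complete a SF-36 quality of life survey". Section 6.8.1 agrees with that second paragraph: "If wound is still closed subject will continue to 6.8.2 below". The SF-36 then follows in 6.8.3.

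If an infection is found at a follow-up visit, 6.7.2 asks for an adverse event form and states that "the subject will be discontinued from the study". Section 6.9 lists infection and osteomyelitis of the study ulcer as exit reasons and ends all study obligations at exit. The discontinuation form (6.10.6) records when and why the subject left.

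On analysis, Section 7 says "Missing data will be ignored in statistical calculations", with the n that fits each statistic. Change in quality of life is tested by repeated measures ANOVA (synopsis) or, as appropriate, a Wilcoxon signed rank test (Section 7).

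**The concern.** A before-after comparison needs two scores from the same subject. If whether the second score exists depends on how the ulcer fared, the comparison describes a selected group. Infection and osteomyelitis are events the protocol expects: 5.1 lists both as treatment risks and 14.2 lists both as reportable. Subjects who leave for these reasons are unlikely to have gained as much in quality of life as those who stay, so leaving them out would probably flatter the mean change. The loss cannot be repaired later, because nothing more is asked of the subject after exit.

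The conflict over reopened wounds adds a second problem. Sites may follow different paragraphs, so the same event would yield a score at one site and none at another. Where the survey is given at a confirmation visit that finds the wound open, a subject who reopens early can also end up with two post-treatment scores. No section says which of them is the score after treatment.

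**Working it through.** **1. The plan's own figures.** The only sample-size figures are exact 95% limits for the closure rate at n = 50. With lower limit = Beta(0.025; x, n−x+1), upper limit = Beta(0.975; x+1, n−x) and x = 12.5, 25 and 37.5, the results are 13.84–39.26%, 35.53–64.47% and 60.74–86.16%. These match the stated limits. They concern closure; the plan has no corresponding figure for the SF-36.

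**2. Exit paths after the index application.**

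| Path | Post-treatment SF-36 | Source |
|---|---|---|
| Open at Week 12 visit | Yes | 6.1, 6.7.4–6.7.5, Table 1 footnote |
| Closed, still closed one week later | Yes | 6.8.1–6.8.3 |
| Reopened at a confirmation visit at or before Week 12 | Still reachable, since the subject returns to follow-up | 6.8.1, 6.7 |
| Closed at Week 12, open at Week 13 | Texts conflict | see step 3 |
| Infection or osteomyelitis of the study ulcer | None called for at exit | 6.7.2, 6.9, 6.10.6, Table 1 |
| Withdrawal, loss to follow-up, death | None called for | 6.9 |

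Infections found at Visit 2 (6.6.3) come before application and hence before enrolment, so they are outside this point.

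**3. Closed at Week 12, open at Week 13.** The wound was closed at Week 12, so 6.7.5 did not apply that day. At Week 13 the synopsis, the first Confirmation Phase paragraph of 6.1 and Table 1 give the survey. The second paragraph of 6.1 and 6.8.1 lead only still-closed subjects to it and send the others back to a follow-up phase whose 12 weeks have already run. On that reading no later visit exists at which the survey could be given.

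**4. Possible size.** The documents give no infection rate, no reopening rate and no SF-36 SD, so every input here is assumed. Let m be the share without a second score and g the amount by which their mean change is worse than that of the measured subjects. Then

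mean change in all = (1−m) × observed mean + m × (observed mean − g) = observed mean − m × g,

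so the measured mean is too favourable by m × g.

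- Low: infection exits 5%, no reopeners, g = 5: 0.05 × 5 = 0.25 points; paired n = 50 × 0.95 = 47.5.
- Middle: 10% and 2%, g = 5 to 10: 0.12 × 5 = 0.6 to 0.12 × 10 = 1.2 points; paired n = 50 × 0.88 = 44.
- High: 20% and 5%, g = 10: 0.25 × 10 = 2.5 points; paired n = 50 × 0.75 = 37.5.

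If the survey is given at every confirmation visit, the reopeners drop out of m and the high case becomes 0.20 × 10 = 2.0 points. If g = 0 there is no bias. For scale, with an assumed SD of change of 10 and 44 pairs, the standard error is 10/√44 = 1.51.

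**The case against.** The strongest reply is that the plan already surveys the main group of treatment failures. Subjects whose wound is still open at Week 12 must complete the SF-36, as the quoted lead-in to 6.7.5 itself shows. A reader might infer that the quality-of-life result omits treatment failures as a class; the documents do not support that, and this part of the reply stands in full.

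A reader might also infer that Week 13 reopeners are certainly not surveyed. That too goes beyond the text. Three places give the survey without condition. The Treatment Phase text of 6.1, which asks for the SF-36 when a wound is unhealed after 12 weeks, could be stretched to cover them as well. The supportable statement is that the passages conflict.

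Nor can every omitted subject be called a failure. The primary endpoint is closure at or before 12 weeks and its wording does not require confirmation, so a wound closed at Week 12 and open at Week 13 literally meets it.

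Further, the size rests wholly on assumptions, including what a point means: 6.10.5 lists eight subscales and two summary measures. Section 7 uses the n available for each statistic, so baseline summaries keep everyone and only the change analyses lose subjects. And this is one secondary objective in a single-arm study without a formal hypothesis.

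These replies narrow the point but do not remove it. None of them supplies a post-treatment score for an infection exit, settles which confirmation paragraph governs, or provides an analysis of the missing scores.

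**Conclusion.** The point holds in a limited form. No section calls for an SF-36 when a treated subject is discontinued for infection or osteomyelitis of the study ulcer, and the instructions for a wound that reopens at Week 13 contradict each other. With missing data ignored, the before-after result leaves out the first group and, on one reading, the second. The loss is related to outcome, so the result is probably somewhat too favourable. The direction is a judgement: it assumes that omitted subjects fare worse.

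The size is unknown. Under the stated assumptions it runs from 0.25 to 2.5 points, with 0.6 to 1.2 in the middle case, which is below the illustrative standard error of 1.51. The primary closure endpoint is not affected. The change is worth making because it is cheap and because scores not collected at exit cannot be recovered.

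**What to change.** 1. **Exit survey.** In Table 1, 6.7.2 and 6.9, add the SF-36 at the visit where an infection or osteomyelitis exit is recorded, when the subject is present. The rules on who is discontinued, and their care, stay as they are.
2. **Confirmation visit.** Reconcile 6.1, 6.8 and Table 1 so that the SF-36 is given at every confirmation visit, whether or not the wound is still closed.
3. **Definition.** In Section 7, define the post-treatment score as the last SF-36 completed after the index MIRODERM application, never the Visit 1 score.
4. **Reporting.** State when each post-treatment score was taken and how many are missing by exit reason. Show the change by outcome group, with a sensitivity analysis restricted to Week 12–13 and confirmation-visit scores.

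The cost is one existing questionnaire for a few subjects, which 6.10.5 allows to be given verbally, and slightly longer exit visits. Some scores will come from earlier weeks, which is why timing is reported and the restricted analysis is added. Withdrawal, loss to follow-up and death will still leave gaps; the count by exit reason makes these visible.
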